- Diagnosis of gastroparesis as documented by gastric emptying scintigraphy (4-hour emptying after a low-fat meal with any combination of 2 and 4 hour retention of >60% and 10% respectively)
- Ongoing symptoms referable to gastroparesis (i.e. nausea and vomiting, bloating, and abdominal pain)
- Exclusion of other causes of symptoms such as mechanical gastrointestinal obstruction, uncontrolled esophagitis, peptic ulcer disease, etc. by standard radiographic or endoscopic tests
- Females will be required to use adequate contraceptive methods during study participation as determined by the Principal Investigator and the study team members

Exclusion criteria

- Another active disorder which could explain symptoms in the opinion of the investigator
- Age < than 18 years
- Pregnancy or nursing
- Previous surgery of the upper gastrointestinal tract including vagotomy
- Another active disorder which could explain symptoms in the opinion of the investigator
- Use of narcotics more than 3 days per week
- Significant hepatic injury as defined by significant alanine aminotransferase (ALT) and aspartate aminotransferase (AST) elevations of greater than 2xULN or a Child-Pugh score of 10 or greater
- Serious systemic disease, such as recent myocardial infarction/unstable angina, decompensated congestive heart failure, severe pulmonary disease with dyspnea at rest, or altered mental status from any cause
- Diabetes as defined by HbA1c >6.5 and/or fasting blood sugar of >125 mg/dL
- Contraindications to pioglitazone such as hypersensitivity or allergy
- Concurrent use of: estradiol, ethynyl estradiol, mestranol, pazopanib, warfarin, digoxin, atorvastatin, ranitidine, gemfibrozil, fexofenadine, midazolam
- Any other condition, which in the opinion of the investigator would impede compliance or hinder completion of the study
- History of bladder cancer or family history of bladder cancer
- Failure to give informed consent

Outcome measures

- **Primary:** The primary outcome measure is a binary (0,1) variable indicating improvement as measured by a decline of 1 or more in the total GCSI score
- Secondary outcome measures will be defined to address the following areas:
 - (1) Gastrointestinal symptoms
 - Subscores for the GCSI: nausea/vomiting, postprandial fullness, bloating
 - Total and Subscores for the GSRS
 NIH Patient Reported Outcome Measurement Information System (PROMIS)

gastrointestinal symptom scales.

- (2) Quality of Life
 - PAGI-QoL
 - SF-36

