- (3) Inflammatory Markers
 - CRP and ESR
- (4) Mood and Behavior
 - Beck Depression Inventory
 - State-Trait Anxiety
- (5) Adverse Events
 - Biochemical tests
 - Symptoms of cardiac or pulmonary disease
 - Any other AE reported or noted throughout the study and follow-up

Justification of sample size

This will be a pilot study recruiting 20 candidates.

Statistical analysis

All analyses will be on an intention-to-treat basis. Patients who do not have any of the decline of 1 or more in the total GCSI score recorded during the period of treatment will be counted as not improved (i.e., 0) for the primary outcome. Comparisons will also be made with baseline total GCSI score and other secondary outcomes. Numerical changes will be analyzed by descriptively comparing the between-treatment group differences in mean and median changes; P-values will be derived from Wilcoxon rank sum tests for comparison of the distribution of changes in each group The two-sided P-values so derived will be reported in the primary results paper of the trial. A two-sided P-value of 0.05 will be considered statistically significant.

Standard treatment recommendations

During the screening period, patients will receive a standardized set of recommendations to include dietary modification. The patient's medications are reviewed to eliminate drugs that might exacerbate the underlying dysmotility disorder or prevent the beneficial actions of a prokinetic agent. Dietary modification and use of pain medications as appropriate are the primary management approaches. If symptoms require further treatment during the trial, patients will be instructed to take rescue medications that they would usually take such as prochlorperazine for nausea and vomiting, and tramadol for abdominal pain. These recommendations have been prepared by the GpCRC Steering Committee as standard of care in the management of patients with gastroparesis or related disorders. This will help ensure that the patients in both treatment groups receive standard of care treatment.

Visit schedule

- Screening: at least 1 visit separated by at least 1 calendar day prior pioglitazone treatment; screening period can last no more than 4 weeks after registration
- Final pre-treatment interview, dispensing of study agent
- Follow-up visits: every 4 weeks after pioglitazone treatment throughout the 12 week study
- Post-treatment: follow-up at **16 weeks**

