As part of the screening process for the PIOGAS trial, the patient must have a standardized 4-hour scintigraphic evaluation of gastric emptying using a low fat Egg Beaters meal that is available for review by the study physician. The standard of care gastric emptying scintigraphy may have been obtained at any time within 2 years prior to the registration date. Patients must also have a normal upper endoscopy within the last 2 years, to rule out other potential causes of symptoms such as mechanical obstruction, inflammatory or other structural lesions of the GI tract or non-gastrointestinal causes. Recording of screening data on trial forms may not start until the patient has signed the PIOGAS trial consent statement. Screening and baseline data collection procedures will include questionnaires, physical examination, various laboratory tests, clinical procedures on patients, and review of the patient's medical chart. Data abstracted from a patient's chart may include laboratory, endoscopy, scintigraphy, and radiology test results. Prior therapy will be reviewed and patients will be asked to stop specific treatments such as antiemetic medications. Baseline and follow up questionnaires can be answered through REDcap.

All participants who sign the consent statement will be registered in the trial database (REDcap). Each participant who starts screening will be accounted for at the end of screening, as either a screening success or a screening failure. A screening failure is defined and a participant who signed the consent form and was registered for the PIOGAS trial data system, but is found to be ineligible prior to start of treatment; screening failures include patients who meet medical eligibility criteria but change their mind and do not consent to participation in the trial. The reason for screening failure will be recorded and keyed in the trial database.

Screening visit: The patient should be in a fasting state (no food or drink after midnight the night before) for this visit. The patient will sign the consent form at or prior to the screening visit and will undergo a history and physical examination to identify other illness and contraindications for participation such as use of antiemetic medications.

In addition, the patient will be provided one week supplies of the Gastroparesis Cardinal Symptom index-Daily Diary (GCSI-DD) for completion each night before bed.

The patient will complete the following questionnaires:

- PAGI-SYM

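### Antiemetics are stopped at screening but allowed as rescue during the trial, and rescue does not enter the primary outcome, so a rescue-assisted fall in GCSI can be counted as a pioglitazone response

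*Combined protocol and SAP*

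**What the plan says.** All references are to the combined protocol and SAP.

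- **Before treatment.** Screening visits and baseline data collection states: "patients will be asked to stop specific treatments such as antiemetic medications". The Screening visit paragraph has the history and examination look for "contraindications for participation such as use of antiemetic medications". The one-week baseline GCSI-DD is issued at this same visit. The Exclusion criteria list does not name antiemetics.
- **During the trial.** Under Standard treatment recommendations, if symptoms need more treatment, "patients will be instructed to take rescue medications that they would usually take"; the examples are "prochlorperazine for nausea and vomiting, and tramadol for abdominal pain".
- **Primary outcome.** Outcome measures defines improvement as "a decline of 1 or more in the total GCSI score". Statistical analysis gives one route to a score of 0, which is having no such decline recorded during treatment. It applies intention-to-treat and does not mention rescue.
- **GCSI content.** Specific Tests and Questionnaires describes nine items, each scored 0 to 5, in three subscales: nausea/vomiting, fullness/early satiety and bloating.
- **What visits record.** Follow-up visits take a medical history and review study drug adherence and tolerance. The Data Collection Schedule has no line for rescue or concomitant medication.
- **Design.** The study is an open-label pilot with 20 patients and one treatment group.

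**The concern.** The primary outcome compares each patient with their own baseline. If antiemetics are off in the baseline week and back on during treatment, part of the fall in the nausea/vomiting items may come from the antiemetic. The outcome definition would still score that patient as improved.

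In a randomised trial both arms would have the same access to rescue, and the comparison between arms would absorb some of this. The Standard treatment recommendations invoke that safeguard by referring to both treatment groups, but the study has only one. What is at stake is whether the response rate, the pilot's main result, can be interpreted. Nightly rescue use that is not recorded at the time cannot be reliably recovered later.

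**Working it through.** **1. Is there a plan figure to reproduce?** No. The sample size of 20 is given without a response rate, effect size, power or success threshold. The point concerns the outcome definition and does not depend on how 20 was chosen.

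**2. The passages side by side.**

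| Stage | Antiemetics | Source |
|---|---|---|
| Screening | Patients asked to stop; use named as a contraindication | Screening visits and baseline data collection; Screening visit |
| Baseline diary week | Not stated whether on or off | No stop date given |
| During the trial | Usual antiemetic allowed if symptoms require it | Standard treatment recommendations |
| Scoring of response | Not considered | Outcome measures; Statistical analysis |

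Nothing in the last row prevents a rescue-assisted fall from scoring 1. Because any qualifying decline recorded during treatment appears to count, a short-lived fall may be enough.

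**3. Weight of one patient.** 1/20 = 5 percentage points.

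**4. Illustrative range.** Let p be the response rate without rescue, f the share of the remaining patients who use rescue antiemetics, and c the share of those users whose GCSI then falls by 1 or more. None of these is in the documents; all three are assumptions.

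Observed rate = p + (1 − p) × f × c. Extra responders = 20 × (1 − p) × f × c.

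- p = 20%, f = 20%, c = 50%: 0.20 + 0.80 × 0.20 × 0.50 = 0.28, or 1.6 extra responders.
- p = 20%, f = 30%, c = 50%: 0.20 + 0.80 × 0.30 × 0.50 = 0.32, or 2.4 extra.
- p = 20%, f = 50%, c = 50%: 0.20 + 0.80 × 0.50 × 0.50 = 0.40, or 4.0 extra.

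Over p = 10% to 40%, f = 10% to 50% and c = 25% to 50%:

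- Lowest: 20 × 0.60 × 0.10 × 0.25 = 0.3 responders (1.5 points).
- Highest: 20 × 0.90 × 0.50 × 0.50 = 4.5 responders (22.5 points).

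**5. What this does to a reported rate.** Suppose 10 of 20 respond and 3 of the 10 owe it to rescue; both counts are assumptions. The rate moves from 10/20 = 50% (exact 95% CI 27.2% to 72.8%) to 7/20 = 35% (15.4% to 59.2%).

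**6. How easily can an antiemetic reach the threshold?** The documents do not say how total GCSI is scored.

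- If it is the mean of the three subscales and only nausea/vomiting moves, that subscale must fall 1 × 3 = 3 points on a 0 to 5 scale. Rescue would then mainly tip patients who had already partly improved.
- If it is the sum of nine items, a 1-point fall in one item is enough.

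**7. Direction.** If the baseline diary week is off antiemetics, the bias is toward response. If rescue is also used in that week, the bias shrinks. The Sample size justification names baseline PAGI-SYM as the primary comparison, and PAGI-SYM contains the GCSI with a 2-week recall. If that is the source and drugs are stopped at the screening visit, the baseline recall would cover days on antiemetics, which works against response.

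**The case against.** **Rescue is already handled by intention-to-treat.** Counting outcomes regardless of rescue is a recognised treatment-policy approach, and stopping prior antiemetics while allowing conditional rescue need not be a contradiction. This stands as a reason to keep the planned primary. It does not let a reader of a single-arm result tell how much of the response came with added antiemetics, and the documents do not say how the stop instruction and the contraindication give way to rescue.

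**The direction is not proven.** A reader might infer that baseline is certainly measured off antiemetics and the response rate certainly inflated. The documents do not support that. No stop date is given relative to the diary week, and rescue during the trial could include screening, since the same section opens with the screening period.

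**Rescue might still be recorded or noticed.** A reader might infer that the plan has no means of capturing rescue use or seeing its effect. That is also too strong. Medical history is taken at every follow-up visit, the case report forms and diary layout are not part of this document, and the nausea/vomiting subscore is a secondary outcome. A fall confined to that subscale would be visible, though it would not prove a rescue effect. What remains is that no dated record is described that could be matched to diary nights.

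**Tramadol is beside the point.** This stands. Abdominal pain is not a GCSI subscale, so the concern rests on the antiemetic alone.

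**A single-arm pilot cannot isolate a drug effect anyway.** True, and the dietary modification introduced at screening is another uncontrolled influence. This limits how much the change can achieve. Rescue is nevertheless an influence that can be measured cheaply.

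**Conclusion.** The concern holds in a limited form. The protocol stops antiemetics at screening, allows them as rescue during the trial, and defines the primary response without reference to rescue. With no control arm, a fall in GCSI helped by a rescue antiemetic can be counted as a pioglitazone response.

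Bias toward response is the likely direction, conditional on the baseline week being off antiemetics. The size cannot be determined from the documents. Each affected patient is worth 5 percentage points, and the assumed ranges give 0.3 to 4.5 extra responders of 20. The larger values are more plausible if total GCSI is a sum than if it is a mean of subscales. The plan sets no success threshold, so the effect is on the reported response rate and its interpretation. This is an inexpensive improvement that should be made before data collection; it does not invalidate the study.

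**What to change.** 1. Add a nightly yes/no line for rescue antiemetic use to the GCSI-DD, in the baseline week and throughout treatment.
2. Keep the planned primary outcome and analysis.
3. Pre-specify which diary nights determine response. The plan defines no such window at present, and the supplementary analysis needs one.
4. Add one pre-specified supplementary analysis that counts as not improved any patient whose antiemetic use on those nights exceeds use in the baseline week, compared as days per week if the two windows differ in length. Patients whose use is unchanged or lower keep their response.
5. Report antiemetic days per week at baseline and on treatment.
6. Analgesic rescue may be recorded descriptively but should not determine response.
7. Reconcile the screening text on antiemetics with the Standard treatment recommendations, including when antiemetics are stopped relative to the baseline diary. Which clinical rule applies is for the study team; none is proposed here.

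Cost: one diary line and one extra analysis. The supplementary response rate will be equal to or lower than the primary one.

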Pioglitazone for Idiopathic Gastroparesis NCT04300127 8/24/2020

Clinical Protocol Synopsis- Pioglitazone for the Treatment of Gastroparesis

Title

Pioglitazone for the Treatment of Idiopathic Gastroparesis (PIOGAS Study)

Type of study

• Open label pilot study

Objective

- The principal objective of this pilot study will be to evaluate whether 8 weeks of treatment of pioglitazone will improve symptoms as measured by the Gastrointestinal Symptom Index Daily Diary (GCSI-DD) in patients with Idiopathic Gastroparesis
- Secondary objectives of this study include:
 - To determine the effects of pioglitazone on other symptoms associated with gastroparesis using the Patient Assessment of Upper Gastrointestinal Symptom Severity Index (PAGI-SYM) and the Gastrointestinal Symptom Rating Scale (GSRS),
 - To determine the effects of pioglitazone on gastric emptying as measured by the ¹³C- Spirulina breath test,
 - To determine the effects of pioglitazone on satiety as measured by a liquid caloric test
 - To determine the effects of pioglitazone on depression and anxiety using the Beck Depression Inventory and State-Trait Anxiety Scores,
 - To determine the effects of pioglitazone on Quality of Life using the PAGI-QoL and SF-36 questionnaire,
 - To determine the effects of pioglitazone on markers of inflammation (CRP and ESR) and serum cytokine levels
 - And to determine the nature and incidence of adverse effects from a 12-week course of pioglitazone.

Treatment group

• Pioglitazone (30 mg po qd)

Population

 Age 18 years or older at registration with nausea, vomiting, and other symptoms suggestive of patients with chronic nausea and vomiting of presumed gastric origin, with symptomatic gastroparesis.

Study duration

- Up to 4 weeks of screening prior to pioglitazone treatment
- 8 weeks of treatment starting at initial dose of pioglitazone
- **4 weeks** of washout period
- Length of recruitment: 16 months

Sample size justification

- Total of **20 patients**
- Primary comparison: Baseline PAGI-SYM score versus 4, 8, and 12 weeks.

Number of clinical centers

- Johns Hopkins Bayview Medical Center.
- Mayo Clinic Scottsdale, Arizona This site will not perform enrollment of patients, It will only intervene as data analysis center under the supervision of [name].
- •

Inclusion criteria

- Age 18 years or older at registration

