Week 4 visit: Medical history including clinical global patient impression (GCPI) questionnaire. The following questionnaires should be completed: Patient Assessment of Upper Gastrointestinal Disorders Symptom Severity (PAGI-SYM), NIH Patient Reported Outcome Measurement Information System (PROMIS) gastrointestinal symptom scales. Review study drug adherence and tolerance of the study drug with the participant. The daily GCSI-DD completed by the patient each night since beginning treatment will be collected by the clinical center staff.

In addition the patient will be provided 4 weeks of GCSI-DD for completion each night before bed.

- Week 8 visit: Medical history including clinical global patient impression (GCPI) • questionnaire. The following questionnaires should be completed: Patient Assessment of Upper Gastrointestinal Disorders Symptom Severity (PAGI-SYM), NIH Patient Reported Outcome Measurement Information System (PROMIS) gastrointestinal symptom scales. Review study drug adherence and tolerance of the study drug with the participant. The GCSI-DD completed by the patient each night since the last visit will be collected by the clinical center staff. In addition the patient will be provided 4 weeks GCSI-DD for completion each night before bed. Laboratory test results that need to be recorded from chart review or obtained as part of screening include: CBC (complete blood count), metabolic panel (sodium, potassium, chloride, bicarbonate, calcium, BUN, creatinine, alanine aminotransferase (ALT), aspartate aminotransferase (AST), magnesium, albumin, total protein). CRP and ESR
- Week 12 visit: Medical history, physical exam including clinical global patient impression (GCPI) questionnaire. The following questionnaires should be completed: Patient Assessment of Upper Gastrointestinal Disorders Symptom Severity (PAGI-SYM), Gastrointestinal Symptom Rating Scale (GSRS), Health Survey (SF-36v2), Beck Depression Inventory (BDI-II), and State Trait Anxiety Inventory (STAI), NIH Patient Reported Outcome Measurement Information System (PROMIS) gastrointestinal symptom scales. Review study drug adherence and tolerance of the study drug with the participant. The GCSI-DD completed by each the patient night since the last visit.

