Anthropomorphic assessments (body weight, body height, body mass index [BMI], waist circumference, hip circumference, vital signs (systolic and diastolic blood pressure, heart rate, respiratory rate, body temperature); and general physical findings will be collected.

• Week 16 visit: This will be a terminal visit. Medical history including side effect or symptom profile, and include a questionnaire for global overall relief of symptoms question and clinical global patient impression question.

PIOGAS Study Data Collection Schedule								
	Screening & Pioglitazone treatment Visits		Follow-up Visits: Weeks from start of treatment					
	Screening	Treatment initiation	4	8	12			
Consent	Х							
Gastric emptying scintigraphy results review	Х							
Baseline medical history	Х							
GCSI-DD	Х		Х					

			N N		
Collection of GCSI-DD			Х	Х	Х
PAGI-SYM questionnaire	Х		Х	Х	Х
GSRS questionnaire	X				Х
SR-36v2 Healthy Survey questionnaire	Х				Х
Beck Depression Inventory-II	Х				Х
State Trait Anxiety Inventory	X				Х
PROMIS NIH scale	Х		Х	Х	Х
Physical exam	Х				Х
Study drug dispensed		Х			
Follow-up medical history, including			Х	Х	Х
review of adverse events					
CBC, CMP	Х			Х	
HbA1c	X				
CRP & ESR	Х			Х	
12-lead EKG	Х				
Pregnancy test	X				

Physical exam includes weight, vital signs (temperature, heart rate, blood pressure) and general physical findings **Complete blood count (CBC)**: white blood cells, red blood cells, hemoglobin, hematocrit, platelets **Complete metabolic panel (CMP)**: sodium, potassium, chloride, carbon dioxide, glucose, calcium, BUN, creatinine, bilirubin, ALT, AST, alkaline phosphatase, magnesium, albumin, total protein

Specific Tests and Questionnaires

- Laboratory Tests: All laboratory test results may be obtained as archival material from the patient's chart or should be collected as part of standard of care during screening. The etiologic tests required once as part of screening include: high-sensitivity C-reactive protein (hs-CRP); sedimentation rate (ESR); complete blood count (white blood cell count (WBC), red blood cell count (RBC), hemoglobin, hematocrit, platelet count); comprehensive metabolic panel (sodium, potassium, chloride, carbon dioxide, calcium, BUN, creatinine, glucose, and liver panel including total protein, albumin, total bilirubin, aspartate aminotransferase, alanine aminotransferase, alkaline phosphatase); and hemoglobin A1c.

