The adverse events reported in placebo-controlled clinical trials of pioglitazone are upper respiratory tract infections, headache, sinusitis, myalgia, tooth disorders, Diabetes Mellitus aggravated, pharyngitis, chest pain, decreased urine output, dilated neck veins, extreme fatigue, irregular breathing, irregular heartbeat, swelling of the face, fingers, feet, or lower legs, tightness in the chest, trouble breathing, weight gain, decreased hemoglobin and hematocrit, elevated liver function enzymes and creatine phosphokinase (CPK).

Adverse events will be evaluated in every follow up visit. A form of Adverse Event will be completed if the candidate complains of any symptom, sign, abnormal assessment or any combination of these. An adverse event can be an expected side effect that is of a serious nature, or an unexpected side effect/event regardless of severity.

This study will monitor and report adverse events to ensure patient safety to IRB and FDA. Signs and symptoms associated with the adverse event will be graded as to severity by the clinical site staff as mild, moderate, or severe using Version 4.03 of the National Cancer Institute's Common Terminology Criteria for Adverse Events (CTCAE).

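### Weight, vital signs and physical examination are planned only at screening and week 12, so under the 8-week regimen none of them is measured on drug

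*Combined protocol and SAP*

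**What the plan says.** **When the examination is done.** The (3) Follow-up visits section lists an examination at one visit only: "Week 12 visit: Medical history, physical exam including clinical global patient impression (GCPI) questionnaire". Body weight, other body measurements, vital signs and general findings are listed under that visit and at screening. The week 4 entry opens "Week 4 visit: Medical history including clinical global patient impression (GCPI) questionnaire" and continues with questionnaires, diary handling and a review of adherence and tolerance. Week 8 has the same content plus CBC, metabolic panel, CRP and ESR. Neither entry lists weight, vital signs or an examination, and nor does the week 16 entry.

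The PIOGAS Study Data Collection Schedule matches the text. Its physical exam row is marked at screening and week 12 only, and the footnote defines the row: "Physical exam includes weight, vital signs (temperature, heart rate, blood pressure) and general physical findings".

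**What the risks are.** The Risks section includes "swelling of the face, fingers, feet, or lower legs, tightness in the chest, trouble breathing, weight gain" among the reported events and also lists dilated neck veins and irregular heartbeat. It has adverse events assessed at each follow-up visit. Cardiac and pulmonary symptoms are an adverse-event outcome under Outcome measures.

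**How long treatment lasts.** The principal objective is to "evaluate whether 8 weeks of treatment of pioglitazone will improve symptoms". The Study duration list gives 8 weeks "of treatment starting at initial dose of pioglitazone" and then 4 weeks "of washout period". The last secondary objective, however, concerns the "nature and incidence of adverse effects from a 12-week course of pioglitazone". Week 12 still includes an adherence review, and the Visit schedule places post-treatment follow-up at week 16.

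**The concern.** The plan collects weight, blood pressure, heart rate and physical findings, names risks that these measurements would detect, and makes adverse effects an objective. Under the 8-week regimen it takes the measurements before exposure and again after washout, but not during exposure. Weight change and distended neck veins are established by weighing and examining the patient, and history covers them only in part.

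Two consequences follow under that regimen. A change that develops on drug and reverses during washout could leave no trace in the measured data. A screening-to-week-12 weight change would describe the patient after washout and could not be read as an on-drug effect; a reader of the results might take a null change as reassurance it cannot give. With a single arm, there is also no control group against which to interpret such a change.

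**Working it through.** The plan states no figure to reproduce here. The check places each visit on the treatment clock and counts the planned measurements.

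**Inputs**
- Time zero is the first day of treatment ((2) Treatment Start Visit).
- Follow-up visits are at weeks 4, 8 and 12 ((3) Follow-up visits).
- Treatment is 8 weeks followed by 4 weeks of washout (Objective; Study duration), or a 12-week course (last secondary objective).
- Weight, vital signs and examination are at screening and week 12 (visit text and schedule).
- Planned sample size is 20.

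**8-week regimen**
- Time off drug at week 12 = 12 − 8 = 4 weeks = 4 × 7 = 28 days.
- On-treatment visits are weeks 4 and 8. Visits with weight, vital signs or examination: 0 of 2.
- For 20 patients: 20 × 2 = 40 planned on-treatment visits, 20 × 0 = 0 with these measurements.

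**12-week reading**
- Time off drug at week 12 = 12 − 12 = 0 weeks, so the examination falls at the end of dosing, day 12 × 7 = 84.
- On-treatment visits are weeks 4, 8 and 12. Visits with the measurements: 1 of 3.
- For 20 patients: 20 × 3 = 60 planned on-treatment visits, 20 × 1 = 20 with these measurements, none before day 84.

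**Planned safety data by visit**

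| Visit | History, adverse events, tolerance | Blood tests | Weight, vital signs, examination | 8-week regimen | 12-week reading |
|---|---|---|---|---|---|
| Week 4 | yes | no | no | on drug | on drug |
| Week 8 | yes | CBC, metabolic panel, CRP, ESR | no | end of dosing | on drug |
| Week 12 | yes | no | yes | 4 weeks after last dose | end of dosing |

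The week 8 blood tests bear on other named risks (lower hemoglobin and hematocrit, raised liver enzymes). They do not measure weight, blood pressure, heart rate or oedema. The plan thus already repeats its laboratory tests at the end of the 8-week course, but not its examination.

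**The case against.** The strongest reply has four parts.

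1. **Safety is monitored on drug.** Adverse events are reviewed at every follow-up visit, tolerance is discussed at weeks 4 and 8, and a form is completed for any symptom, sign or abnormal assessment. Patients can report swelling, breathlessness, chest tightness and even weight gain, and the cardiac and pulmonary outcome is worded in terms of symptoms. The week 8 blood tests could themselves trigger a form. This stands. A reader might infer that these risks go unmonitored during dosing, or that nothing at weeks 4 and 8 could be abnormal. The documents contradict both. What is absent is measured weight, vital signs and examination, and patient report does not replace them.

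2. **Dosing may run to week 12.** The safety objective, the week 12 adherence review and the week 16 post-treatment visit all point that way. This also stands, and the count of 0 of 2 therefore holds only for the 8-week regimen. On the 12-week reading the gap narrows to one late measurement but does not close.

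3. **Masking by washout is not shown.** A reader might infer that the trial would report little or no weight or fluid effect. The documents do not support this: they give no rate at which weight gain or oedema resolves in 4 weeks, they plan no weight-change analysis, and symptoms reported at weeks 4 or 8 would still be recorded. Masking is possible, but its size is unknown.

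4. **Telemedicine.** The section on screening and baseline data collection allows remote visits so as to limit research-only attendance, so attendance in person at weeks 4 and 8 cannot be assumed. This is a real cost of the change.

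**Conclusion.** The point holds in a limited form. Under 8 weeks of treatment and 4 weeks of washout, none of the 2 on-treatment visits has a planned weight, vital-sign or examination measurement, and the only one after baseline comes 28 days after the last dose. Under the 12-week wording, 1 of 3 on-treatment visits has it, at the end of dosing. The passages on duration conflict and must be reconciled; this review does not say which is right.

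The 8-week count treats the week 8 visit as on treatment, at the end of dosing. The effect on the reported results cannot be sized, because the documents give nothing on how often a weight or fluid effect would appear and then reverse. The primary symptom outcome is not affected. The weakness lies in the objective data behind the safety objective and is worth correcting before enrolment.

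**What to change.** - Reconcile the 8-week and 12-week treatment passages (Objective, Study duration, Visit schedule, week 12 visit text), so that it is clear which visits are on drug.
- Align the physical exam row with the exposure period. Record the weight, vital signs and general physical findings already defined in the schedule footnote at existing on-treatment visits: at minimum week 8, where blood is already taken, and preferably also week 4. Enter this in both the schedule and the visit text.
- State that weight change is summarised from screening to the last on-drug visit, with any post-washout value reported separately.

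Any clinical action on a finding is for the sponsor to set.

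**Cost:** an amendment to the schedule and visit text, and one or two added examinations per patient at visits already planned (20 × 1 = 20 to 20 × 2 = 40 in all). The main downside is that those visits become harder to hold entirely by telemedicine.
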